Study Protocol: Decision Making Support for Parents and Caregivers

Study Site:

Duke University Hospital
[name]
[name]

Principal Investigator:

[name]
Department of Pediatrics and Population Health Sciences
[name]
[name]

ClinicalTrial.gov identifier: NCT05733975

IRB: Pro00111995; March 20, 2023

Study Title: Decision Making Support for Parents and Caregivers**Short Title: Decision Making Support****Study Objective.**

To determine the feasibility and acceptability of a tool to support decision making for parents of critically ill children.

Study Overview.

The feasibility study will use a single-arm design. All critically ill infants for whom a serious decision is anticipated will be screened for enrollment. We will enroll up to 40 infants, their parent(s), and their clinician(s). A study team member will deliver the tool, discuss its use with parents, and answer parent questions as they arise. We will survey parents at baseline. Parents and clinicians will be surveyed and interviewed after utilizing the tool.

Measures.

Prior to implementation of this decision aid in a prospective randomized trial, we must first determine whether 1) study procedures are feasible and 2) the intervention is acceptable to parents and clinicians.

Feasibility will be defined as 1) enrollment rate of $\geq 50\%$ and 2) complete data collection rate of $\geq 80\%$. Parent and clinician acceptability will be measured using self-report survey measures, adapted from prior work. Additional outcomes will include preparation for decision making, parent decisional conflict, regret, and satisfaction, perception of feeling heard and understood, and psychological distress. Preparation for decision making will be measured using the PrepDM. Decisional conflict and regret will be measured by the Decisional Conflict Scale (DCS) and the Decisional Regret Scale (DRS); perception of feeling heard and understood will be measured by the Feeling Heard and Understood Scale (FHAU); parent psychological distress will be measured using PROMIS-29.

Data collection.

The infant's chart will be reviewed and relevant data extracted. We will also document recruitment feasibility data. Parent baseline surveys will include demographic information and measures of psychological distress. Post-intervention surveys will be given to parents and clinicians following use of the tool. Clinician surveys will include measures of decision aid acceptability. Parent surveys will include measures of decision aid acceptability, decisional satisfaction, conflict and regret, perception of feeling heard and understood, preparation for decision making, and psychological distress.

Parents and clinicians will be invited to complete semi-structured interviews, with content targeting acceptability of the decision aid. Survey data will be collected and stored via REDCap. Qualitative data will be analyzed using NVIVO.

Study participants.

Study participants will include infants, parents, and clinicians. Study team members will screen unit lists for potential eligible patients.

Infant inclusion criteria will include 1) age < 1 year, 2) admission to a critical care unit, and 3) an anticipated serious health care decision, defined as 1) a decision about

initiating, not initiating, or withdrawing life sustaining treatment or chronic life-sustaining treatment (e.g. tracheostomy) and/or 2) a decision about major surgery and/or medical therapy.

All parents of eligible infants will be considered for inclusion. Parent exclusion criteria will include 1) age < 18 years, 2) hearing or speech impairment, and 3) non-English speakers.

All clinicians of eligible infants will be considered for inclusion.

Subject Recruitment and Compensation.

We anticipate up to 40 infants, 60 parents, and 40 clinicians will be enrolled in this study.

Patients and parents: We will recruit from the Duke Intensive Care Nursery, Pediatric Intensive Care Unit, and Pediatric Cardiac Intensive Care Unit.

A study team member will communicate with the unit about 1) eligible patients and 2) approaching the family about their willingness to speak with research staff about the study. A waiver of HIPPA authorization has been requested to allow identification of prospective participants. A member of the study team will approach eligible families to introduce the study to the family. For infants enrolled, parents will be compensated \$100 for completion of all study procedures. Clinicians will be compensated \$50 for completion of all study procedures.

Study Intervention.

The intervention includes a paper-based decision support tool. This decision guide includes content related to decisional awareness, values clarification, and a series of question prompts. This intervention will be introduced to participants by a study team member, who will remain available with parents as they review and complete the tool. The tool asks parents to consider which values matter most to them and to identify questions they would like to ask the clinical team. Following completion of the tool, a study team member will ask parents if they would like their answers shared with their clinical team. If the parent would like to share their responses, the study team member will share a copy of parent responses with clinicians caring for the patient and their family.

Risk-benefit assessment

Benefits. There will be no direct benefits to the participants in the study. The potential benefit to future parents and clinicians is substantial because of the potential for this study to lead to the development of interventions to improve shared decision making for infants and children with life-threatening conditions. Therefore, the risks of this study, which we anticipate to be minimal, are reasonable in relation to its anticipated benefits.

Adverse events. The principal investigator or the clinical study staff will record and follow all adverse events that occur. Data describing adverse events will be collected and reported to the IRB.

Confidentiality and data security. We believe this study poses minimal risks to participants. See additional sections for procedural information concerning data storage, privacy, confidentiality, and safety monitoring.

Parent distress. It is possible that intervention delivery or study procedures, including participant interviews, could increase parent distress. Previous research has shown that

interviews do not increase grief, and that families are glad to have participated in studies involving interviews about highly emotional topics. We will use several strategies to minimize the possibility of increasing distress, including 1) keeping the interview flexible so that when emotional responses such as anger or crying occur, the interviewer may offer rest breaks and direct the interview in and out of the sensitive area, and 2) providing immediate therapeutic intervention when needed. A study team member with interview experience or the study PI will perform the interviews. Should a parent become upset during an interview or survey completion, the study team member collecting the data will allow the parent to stop and encourage them to talk about their feelings. If a parent remains upset, the research staff member will stay with the parent and help them to contact the social worker or a community mental health professional about their concerns. As part of routine clinical care, a social worker is assigned to each patient and family. After each parent interview, parents will be reminded that if they have concerns they wish to discuss, they can contact their social worker, hospital chaplain or personal clergy, or community mental health professional. The parents will be given information on how to contact other resources if necessary or, if they prefer, the research staff will contact a professional for them. For concerns or questions about the study, parents will be given phone numbers for the investigators.

Parent burden. We anticipate that tool completion will require 15-20 minutes of participant time. Parent interviews are expected to last approximately 30-45 minutes. Clinician interviews are expected to last approximately 15 - 30 minutes. This time commitment may be a burden for some participants.

Data and safety monitoring

We believe this study will infer minimal risk to participants. Interval data analysis will be performed midway through study completion. Data monitoring, including ensuring audio-recordings are transcribed in a timely manner, will be confirmed monthly by the principal investigator and/or study coordinator. For the audio recordings, we will use a Duke-approved transcription service. For the purposes of our study, “de-identification” will involve the removal of all identifiers outlined by the HIPAA privacy rule. Qualitative software will be used to analyze de-identified transcripts.

Analysis files will be permanently stored on the Duke Server. During the analysis phase, de-identified analysis files may additionally be stored on Duke Box or a Duke University or Duke Health System computer, and uploaded to the Duke server daily.

Consent process.

The consent process will be completed by the principal investigator, clinical research coordinator, or clinical research specialist on the study team. There is no time limit to the consent discussion. We are open to answering any potential questions that may arise when we present the study information to parents or clinicians.

The consent process will occur in the Neonatal Intensive Care Unit, the Pediatric Intensive Care Unit, or the Pediatric Cardiac Intensive Care Unit. The parent/legal guardian may be consented over the phone or by using an e-consent. The phone consent process will take place in those situations where attempts to find families in the neonatal intensive care unit have failed. With the use of phone consent or an e-consent all efforts will be made to provide a copy of the consent to parents either by fax or email before reading the consent. A telephone script will be used to introduce the study and then the consent form will be read to the parent or sent via email as an e-consent.

To mitigate the risk of loss of confidentiality, all patient and clinician data will be fully de-identified, with a participant ID number assigned in the place of any identifiers. This ID number will be linked to identifying information only in a secure, separate file for the duration of the study period and analysis, to allow follow-up clinical information to be collected as needed.

Participants can contact the PI or members of the study team with any questions that arise. In addition, given that this study has multiple points of contact, participants will have additional opportunities to raise questions throughout the study period.

We will maintain a high level of sensitivity to passive refusal, so prospective participants who do not show active interest will not be enrolled in the study.

Privacy and confidentiality.

All patient and physician data will be de-identified, with a participant ID number assigned in the place of any identifiers. This ID number will be linked to identifying information only in a secure, separate file for the duration of the study period and analysis, to allow follow-up clinical information to be collected as needed. All recordings will be transcribed and de-identified.

Audio-recordings, transcriptions, and other data will be securely stored on a Duke server accessible to the research team. Audio recordings will be reviewed by a Duke-approved transcription service to de-identify audio recordings. Paper documents will be kept in a locked cabinet in an access controlled area.

## 1. Study Overview

### Background/Introduction

The study is a single arm intervention trial for assessing the feasibility and acceptability a decision guide for parents of critically ill infants.

### Study Objectives, Aims, and Hypotheses

Primary/ Secondary Outcomes	Aim/Objective	Hypothesis
Primary	Compute enrollment rate.	We expect the proportion of enrolled infants to be at least 50%.
Primary	Compute complete data collection rate.	We expect the proportion of enrolled families with data collected to be at least 80%.
Secondary	Describe decision aid acceptability, stratified by parent and clinician.	Descriptive objective, no hypothesis testing
Secondary	Describe pre- and post- parent psychological distress, stratified by parent.	Descriptive objective, no hypothesis testing
Secondary	Describe pre- and post- decision (as appropriate) outcomes, stratified by parent.	Descriptive objective, no hypothesis testing
Sample description	Describe infant characteristics, parent demographics, and clinician demographics.	Descriptive objective, no hypothesis testing

## 2. Study Population and Data Source

### Study Design

- Single arm design, study team will deliver a tool to be used by parent(s) to help guide them in decision making
- Tool includes a brief introduction to the tool and decision-making, a values clarification exercise, and a question prompt list
- Study will include: critically ill infants, their parent(s), and clinicians

## **Inclusion Criteria**

- Infant inclusion criteria will include
  1. Age < 1 year
  2. Admission to a critical care unit
  3. Anticipated major decision

## **Exclusion Criteria**

- Parent exclusion criteria will include 1) age < 18 years, 2) hearing or speech impairment, and 3) non-English speakers.

## **Data Acquisition**

- Data source: REDCap
- REDCap project name and ID: Decision Making PID 14854

## **3. Outcomes, Exposures, and Additional Variables of Interest**

### **Outcomes**

Outcome	Definition/Descriptions	Variables and Source
Enrollment rate	Percentage of eligible infants enrolled.	screening log
Complete data collection rate	Complete data collection defined as all eligible infant, parent, and clinician data points collected for a given case; data points for which the participant withdrew prior to relevant data collection excluded	data collection log
PrepDM score	The preparation for decision making (PrepDM) scale evaluates parents' perceptions of how useful the decision aid was in preparing them to communicate with their child's health care team and make a decision. The 10-item survey uses a 5-point Likert scale. In accordance with the user manual and other studies, we will convert item responses to integers from 1 to 5, calculate the average, subtract 1 from average, and multiply by 25 to give a final score from 0 to 100. Higher scores indicate a higher perceived level of preparation for decision making.	prepdm_score (to be derived)  Components: decision_present, decision_prep, consider_pros_cons, importance_pros_cons, depends_values, organize_thoughts, decision_involvement, questions_to_ask, discuss_values, prep_future_convos

Found this decision guide to be helpful		guide_helpful
would recommend this decision guide to other parents making decisions about their child's health care		rec_to_parents
would use this decision guide again if I need to make future decisions about my child's health care		would_use_again
Promis t-score	We will measure scores for the following PROMIS domains: Short Form v2.0 Physical Function 4a, Short Form v1.0 Emotional Distress - Anxiety 8a, Short Form v1.0 Emotional Distress - Depression 8a, Short Form v1.0 Fatigue 4a, Short Form v1.0 Sleep Disturbance 4a, Short Form v2.0 Ability to Participate in Social Roles and Activities 4a, Short Form v1.1 Pain Interference 4a, and Numeric Rating Scale Pain Intensity 1a. The default calibration sample will be used for all scores.	stress_promis_tscore (to be derived)
Family satisfaction in the intensive care unit (FS-ICU)	The decision making subscale of the FS-ICU is a 10-item survey that measures family surrogates' satisfaction with the decision making process in the ICU using 5-point Likert-type response formats. Families are asked to rate their satisfaction with communication from the health care team, the quality of the information they received, and how included and supported they felt in making medical decisions. In accordance with the survey's user manual and other studies, we will convert all item responses to integers from 0 to 4, calculate the average, and multiply by 25 to give a final score from 0 to 100. Aligning with prior studies from our group and others, a subscale score $\geq 75$ will indicate a high level of satisfaction with decision making.	fs_icu (to be derived)

Decisional regret score	The DRS is a 5-item survey that measures remorse or distress following a health care decision. Parents are asked to rate their agreement level with statements that express the presence or absence of regret, with 5 response options ranging from “strongly agree” to “strongly disagree.” In accordance with the survey’s user manual and other studies, we will convert all item responses to integers from 0 to 4, calculate the average, and multiply by 25 to give a final score from 0 to 100. Aligning with prior studies from our group and others, a score >25 will indicate a high level of decisional regret.	drs_score (to be derived)  Components: drs_decisions, drs_regret, drs_again, drs_harm, drs_wise
Decisional conflict score	The DCS is a 16-item survey that measures parents’ state of uncertainty about making health care decisions. Parents are asked to rate their agreement level with statements that relate to 5 domains of decisional conflict: being informed, support, effective decision making, uncertainty, and values clarity. In accordance with the survey’s user manual and other studies, we will convert all item responses to integers from 0 to 4, calculate the average, and multiply by 25 to give a final score from 0 to 100. Aligning with prior studies from our group and others, a score >25 will indicate a high level of decisional conflict.	dcs_score (to be derived)  Components: hard_v2, unsure_v2, clear_v2, awarechoice_v2, benefits_v2, risks_v2, advice_v2, importbene_v2, importrisk_v2, riskbenefit_v2, pressure_v2, amount_v2, informed_v2, selfdecision_v2, stick_v2, satisfied_v2
Feeling heard and understood (FHAU) score	The 4-item FHAU scale measures parents’ experience of feeling heard and understood by their infant’s health care team using 5-point Likert-type response formats. In accordance with the user manual and other studies, we will use “top box scoring” for each item that defines “completely true” (i.e., the top box response) as passing, where 1 = passing and 0 = not passing. For each individual, we will average the number of top-box responses (up to 4) to estimate their proportion of Feeling Heard and Understood. We will also use descriptive statistics to calculate the total number of participants who responded “completely true” or “very true” for each item.	fhu_score (to be derived)  Components: heard_understood, interests_first, interests_first, understood_values

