### Decision aid acceptability, Psychological stress, and Decision outcomes

Secondary outcomes include 1) parent and clinician acceptability of the tool, 2) preparation for decision-making, as measured by the Preparedness for Decision-making Scale (PrepDM), and 3) parent psychological distress, as measured using the PROMIS. Parent and clinician acceptability will be measured using self-report questions. Additional measured outcomes include parent decisional conflict, regret, and satisfaction. Decisional conflict and regret will be measured by the Decisional Conflict Scale (DCS) and the Decisional Regret Scale (DRS). Satisfaction with decision-making was measured using the Family Satisfaction-ICU decision-making subscale.

Decision aid acceptability will be summarized separately by parent, mother and father, as well as clinician. Pre- and post-intervention parental psychological stress and decision outcomes will be described for self-identified mothers and fathers separately.

Categorical characteristics will be summarized as frequency and percent, continuous characteristics will be summarized as mean, standard deviation, median, Q1, Q3, and range. A list of all reported variables can be found in the table shells in **section 5**.

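### The SAP's variable list for the four-item Feeling Heard and Understood score names only three distinct variables, because one name is entered twice

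*SAP*

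**What the plan says.** The FHAU row of the Outcomes table (SAP section 3) contains four statements that bear on this point.

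- Number of items: "The 4-item FHAU scale measures" the parents' experience of the care team.
- Score: each item is coded 1 for the top response and 0 otherwise, and then "we will average the number of top-box responses (up to 4) to estimate their proportion of Feeling Heard and Understood".
- Item-level summary: "We will also use descriptive statistics to calculate the total number of participants who responded" with either of two named favourable answers, item by item.
- Components of `fhu_score`, which is marked as a variable to be derived: "heard_understood, interests_first, interests_first, understood_values".

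Three other outcomes in the same table have a component list. PrepDM, stated as 10 items, has "decision_present, decision_prep, consider_pros_cons, importance_pros_cons, depends_values, organize_thoughts, decision_involvement, questions_to_ask, discuss_values, prep_future_convos". The Decisional Regret Scale (DRS), stated as 5 items, has "drs_decisions, drs_regret, drs_again, drs_harm, drs_wise". The Decisional Conflict Scale (DCS), stated as 16 items, has "hard_v2, unsure_v2, clear_v2, awarechoice_v2, benefits_v2, risks_v2, advice_v2, importbene_v2, importrisk_v2, riskbenefit_v2, pressure_v2, amount_v2, informed_v2, selfdecision_v2, stick_v2, satisfied_v2".

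SAP section 4 adds: "A list of all reported variables can be found in the table shells in" section 5. There, Table 7 has a single row for the FHAU score.

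**The concern.** The definition and the variable list in the same table row cannot both be followed. The definition needs four different items, but the list supplies three and repeats one. The list is the part of the SAP that tells a programmer which fields to read, so it matters that it is right.

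A program that follows the list gives one item double weight and ignores another. The result is still a plausible number between 0 and 1, so nothing in the output would reveal the error. The per-item counts promised in the same row would also lack the fourth item if they were taken from this list.

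The fourth item cannot be recovered from the documents. The protocol names the FHAU scale in its Measures section without listing items. The outcome narrative in SAP section 4 does not mention FHAU, and the Table 7 shell shows only the total score.

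**Working it through.** **Step 1. Count the names.** Stated item counts and lists come from the Outcomes table in SAP section 3.

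| Scale | Items stated | Entries listed | Distinct names |
|---|---|---|---|
| PrepDM | 10 | 10 | 10 |
| DRS | 5 | 5 | 5 |
| DCS | 16 | 16 | 16 |
| FHAU | 4 | 4 | 3 |

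The stated count is reproduced for the first three scales and not for FHAU. The FHAU list still has four intact, comma-separated slots, and nothing suggests redaction or a broken table. This looks like a name repeated by mistake.

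**Step 2. Compare the score as listed with the score as defined.** Let h, i and u be the top-box indicators (0 or 1) for `heard_understood`, `interests_first` and `understood_values`, and let m be the indicator for the unnamed fourth item.

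- As defined: (h + i + m + u)/4
- As listed: (h + i + i + u)/4 = (h + 2i + u)/4
- Difference, listed minus defined: (i − m)/4

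Over the 2 × 2 × 2 × 2 = 16 patterns, with 4 combinations of h and u for each pair (i, m):

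- i = m: difference 0, in 2 × 4 = 8 patterns
- i = 1, m = 0: difference +0.25, in 4 patterns
- i = 0, m = 1: difference −0.25, in 4 patterns

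Two examples:

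- A parent with h = i = u = 1 and m = 0 scores (1 + 2 + 1)/4 = 1.00 instead of 3/4 = 0.75.
- A parent with only m = 1 scores 0 instead of 0.25.

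In each case the error is one full step on the five-value scale.

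**Step 3. Effect on group summaries.** The mean shifts by 0.25 × (p_i − p_m), where p_i and p_m are the top-box proportions of the repeated and omitted items. The documents give no item-level proportions, so the gaps below are assumptions:

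- Gap 0: shift 0
- Gap 10 percentage points: 0.25 × 0.10 = 0.025
- Gap 30 percentage points: 0.25 × 0.30 = 0.075

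No individual score moves by more than 0.25, so no median, Q1 or Q3 can move by more than 0.25.

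**Step 4. A different reading of the list.** A programmer might notice the repeat, drop it, and average the three remaining variables. With s = h + i + u, the difference is s/3 − (s + m)/4 = s/12 − m/4. This is zero only when s = 0, m = 0 or s = 3, m = 1, so it is nonzero in 14 of 16 patterns: ±0.083 in 6, ±0.167 in 6 and ±0.25 in 2. This departs from the written rule of up to four responses. It is shown only because two programmers could get different scores from the same row.

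**The case against.** The strongest reply is that the scoring rule itself is right. The row says four items, top-box coding and up to four responses, and the list keeps four slots, so only one name is wrong. The SAP also does not depend on component lists alone: FS-ICU and the PROMIS scores have none, and the Data Acquisition section identifies the REDCap project in which the field can be looked up. An analyst building a four-item score would probably see the repeated name and correct it. On that view this is proofreading, and every error figure above assumes literal coding against the written definition.

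Most of that stands. The documents do not show that the mistake would reach a result, and the actual error may be zero. It does not make the list correct, however. For FHAU the SAP chose to specify the components, and as specified they do not yield the score it defines.

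Two stronger readings should be resisted.

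- A reader might infer that the fourth item was never collected, or that REDCap has no field for it. The documents say nothing to that effect, and a repeated name in a four-slot list is better explained by a slip.
- A reader might take the missing FHAU item rows in Table 7 as further evidence. They are not: that table gives no item rows for DRS or FS-ICU either, and only subscales for DCS. It merely means that the shells do not supply the missing name.

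**Conclusion.** The component list is wrong as written: it has three distinct variables for a four-item score. Coded literally, it misstates an individual's score by 0.25 in 8 of 16 response patterns, 4 too high and 4 too low. That is a count of patterns and says nothing about how often they would occur. The resulting shift in a group mean depends on an unknown gap between two items. For assumed gaps of 0 to 30 percentage points it runs from 0 to 0.075. All of this is conditional on the list being followed literally, and the error is zero if the intended fourth variable is used.

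The point is minor. The SAP's objectives table makes the decision outcomes descriptive, without hypothesis testing. The FHAU score enters neither the enrollment rate nor the complete data collection rate, and no threshold or decision rests on it. The documents do not support a claim that the scoring method is faulty, that data are missing, or that any reported result is wrong.

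**What to change.** In the FHAU row of the Outcomes table (SAP section 3), replace the second `interests_first` with the REDCap variable name of the fourth FHAU item. Take the name from the data dictionary, and confirm in the same check that four separate FHAU fields exist. Use the corrected list for both `fhu_score` and the per-item counts.

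The cost is one variable name in the SAP. The scoring rule, the table shells and data collection do not change. The SAP labels `fhu_score` as to be derived, but the documents do not show whether it has since been programmed. If it has, the code should be checked against the corrected list and the score rerun if it used the repeated name.
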